Infección de Amor (Love Infection): Online Delivery and Pilot Testing of a Dramatized Story Intervention (Telenovela/Soap Opera) for HIV Prevention Among Latinas in North Carolina

NCT number NCT05358366

Document Date 04/03/2022

Infección de Amor (Love Infection): Online Delivery and Pilot Testing of a Dramatized Story Intervention (Telenovela/Soap Opera) for HIV Prevention Among Latinas in North Carolina

Study Protocol

Unique Protocol ID: 21-3214 NCtracs # NCT05358366

Date: 4.3.22

Study Description

The study includes women between 18 to 44 years old. We will enroll 66 participants with the aim of testing the feasibility, acceptability of the IA intervention (four telenovela episodes), assessment of the mechanisms of action (self-efficacy, narrative engagement, and emotional elicitation) and conduct a randomized controlled pilot study to examine the change in primary outcomes (condom use, HIV testing, Pre-exposure Prophylaxis [PrEP] awareness and use) and secondary outcomes (Substance abuse (SA), intimate partner violence (IPV), and depression comparing 33 intervention- and 33 control Latinas at baseline (T1, pre-intervention), T2 (immediately post-intervention, 1 month) and T3 (3 months after the end of the intervention, with no intervening contact with study staff).

Participants will be asked to: (1) attend to a one hour-meeting with the research team to complete a baseline survey and receive an orientation about the use of the telenovela website, (2) access the telenovela website once a week for 4 weeks to watch a telenovela episode and answer some questions about the episode (one hour each week, 4 in total), (3) complete a survey (on their own) one-month after the baseline survey, and (4) complete another survey (on their own) 4-months after the baseline survey. Participants will be interview by the research team using a structured survey in the first meeting (baseline survey) and then they will complete the surveys (1-month and 4-months after baseline) on their own. Participants can request help to complete these surveys (online using zoom or face to face if needed).

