A copy of the ICF will be given to them. This study will focus on Spanish speaking Latinas, but since some Latinas prefer to read in English, participants will have the option to choose the preferred language for the ICF process and the written consent.

Subjects

We will enroll 66 Latinas ages 18-44 years who report sexual activity with a man in the last 6 months, have internet access from any device, and reside in NC. The research team is bilingual and will be able to assist women if they have questions about the study.

Study procedures will be conducted in English and/or Spanish according to participant's preference. Recruitment and screening will be led by a bilingual (English and Spanish) study personnel. Participants will be asked their preferred language at the time of recruitment. All study materials, including information and consent forms, questionnaires, and recruitment ads, will be translated and available in Spanish. Any direct interaction with non-English-speaking participants will be available in Spanish.

Describe the study design. List and describe study procedures, including a sequential description of what subjects will be asked to do, when relevant

The study includes women between 18 to 44 years old. We will enroll 66 participants with the aim of testing the feasibility, acceptability of the IA intervention (four telenovela episodes), assessment of the mechanisms of action (self-efficacy, narrative engagement, and emotional elicitation) and conduct a randomized controlled pilot study to examine the change in primary outcomes (condom use, HIV testing, Pre-exposure Prophylaxis [PrEP] awareness and use) and secondary outcomes (Substance abuse (SA), intimate partner violence (IPV), and depression comparing 33 intervention- and 33 control Latinas at baseline (T1, pre-intervention), T2 (immediately post-intervention, 1 month) and T3 (3 months after the end of the intervention, with no intervening contact with study staff).

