Baseline survey. If potential participants meet the inclusion criteria, they will be asked to attend to a one hour-meeting with a member of the research team to sign the informed consent, complete a baseline survey and receive an orientation about the use of the telenovela website https://www.infecciondeamor.com/. After participants complete the survey, they will be randomized by a member of the research team to the intervention or control group. The research team member will explain the following activities they have to complete according to the group they will be assigned. If they are randomized to the control group, the orientation to the website will be delayed until they complete the 4-month post baseline survey. The survey will be available in Qualtrics and only the members of the research team will have access to the survey.

- **Intervention group:** 33 Latinas will view four IA intervention episodes, one per week. Participants will receive an email to their preferred email address with a password to access to the episode on the IA's website: https://www.infecciondeamor.com/
 - Each 10-minute episode can be watched more than once during the week and presents a situation with notable HIV risk and ways the characters avoided risk (e.g., condom use) or confronted consequences of poor practices (e.g., HIV infection). The one-week time frame for each episode is needed to provide time to review and reflect about IA's content and modify HIV prevention behaviors. It will also allow Latinas to obtain information and support from the team and referral if needed. This time frame was effective to improve behaviors in our previous studies.
 - After each episode, participants will complete a survey (on their own) on the telenovela website. This post episode survey includes questions about the mechanisms of action of the telenovela. (self-efficacy, narrative engagement, and emotional elicitation)
- Control group: A wait-listed control group of 33 Latinas will receive IA in the same manner as the intervention group after completing T3 data collection. Latinas will be informed at recruitment of this group condition and the study randomization. During the three-month waiting time, we will call participants on a monthly basis to encourage participation and refer to services if needed.

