Follow-up surveys. Participants will answer a (one-month after baseline) survey, and complete another survey (on their own) 3-months. Participants will complete these surveys (1-month and 4-months after baseline) on their own. Participants can request help to complete these surveys (online using zoom or face to face if needed). We will not record the zoom meeting if we conduct the surveys using zoom. A description of the study measures is provided below.

Infección de Amor website. The PI with a website developer and [name] developed the IA intervention delivery website. The website provides: a) access to the four intervention episodes 24/7 from any location or type of device (e.g., cellphone, laptop) since it will be mobile optimized (all the episodes are password protected); b) questionnaires for data collection deployed via Qualtrics; c) a contact section in case participants have technical problems or need to contact the research team; and d) a section with community resources, services, and referrals. We will use secure and private servers and communication channels such as OneDrive to store and to exchange information.

The intervention website is accessible only to study participants in English and Spanish. The intervention participants will access telenovela episodes, available in Spanish or English, at their preferred time and place using a website accessible through any device since it will be mobile optimized. A new episode of IA will be available each week. Women will be instructed to watch an episode as many times as they want during the week, but they need to answer a post episodeviewing survey after viewing it the first time. Also, they will be able to pause or stop the episodes at any time if they need to take a break or stop watching for any reason. Women will be advised to watch the episodes alone. Prior episodes will remain available after a new episode is released. Each episode has an opening that introduces the characters and then the content of the telenovela.

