- 2. Participants will only be allowed to join the meeting after the host (either the PI, co-Is or project coordinator) has arrived. In addition, we will use the waiting room feature of Zoom to keep participants in a waiting area until the host is ready for them.
- 3. We will lock down the meeting once every expected participant has arrived. This lock down will prevent others from joining, even if meeting IDs or access details have been leaked.
- 4. For each meeting, a randomly generated meeting ID will be created. Meeting IDs will be sent to participant's email or through text messaging.

Intervention website. The intervention website will not have any personal information from participants. Participants will access to the episodes using a password.

Monitoring. The PI will provide ongoing supervision and training to essential study staff at weekly meetings, which will also ensure continued compliance with data safety protocols. The Investigator will also discuss human subjects' issues at weekly meetings. Participants in human subjects' research inevitably give up some privacy to share data about their individual experiences; however, we believe our data safety and monitoring plan will minimize the risks of any further breach of privacy or confidentiality. The Investigators will be responsible for ensuring that study protocols for maintaining confidentiality are followed.

Statistical Analysis Plan. For Aim 1 and Aim 2 data, we will conduct descriptive analyses of the outcome measures (e.g., the mean and standard deviation for continuous variables and frequency and proportion for categorical variables). To examine the intervention effect on HIV prevention in Aim 2 data analysis, we will adopt multiple mixed-effects models to analyze the data. Specifically, we will include behavioral outcomes (e.g., substance abuse) as the dependent variable. In contrast, the treatment assignment status (intervention or control), age, education level will be included as the fixed effect terms. The subject-level cluster effect following a normal distribution with a mean zero will serve as the random effect term. We will also consider

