different covariance structures among repeated measurements and conduct model selection to determine the optimal model and covariance structure for the data, as in our early published work. Alternatively, if the model does not converge, we will adopt an ANOVA model to investigate the intervention efficacy at each measurement time point. Though the intervention efficacy will be evaluated across several different outcomes in the Aim 2 data analysis, multiple comparisons will not be adjusted since our goal in this pilot study is to collect preliminary data to design future R01 study and proposal submission.

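### The Aim 2 mixed model names no visit, treatment-by-visit or baseline-outcome term, so no T2 or T3 treatment contrast is prespecified

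*Combined protocol and SAP*

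**What the plan says.** The Study Description, repeated in the study design section, sets out to "examine the change in primary outcomes (condom use, HIV testing, Pre-exposure Prophylaxis [PrEP] awareness and use" and compares 33 intervention women with "33 control Latinas at baseline (T1, pre-intervention), T2 (immediately post-intervention, 1 month) and T3", the last of these three months after the intervention ends. The baseline survey precedes allocation: "After participants complete the survey, they will be randomized by a member of the research team to the intervention or control group". Of the follow-up surveys the protocol says "Participants will complete these surveys (1-month and 4-months after baseline) on their own".

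For Aim 2 the Statistical Analysis Plan specifies a mixed model in which "the treatment assignment status (intervention or control), age, education level will be included as the fixed effect terms". It adds: "The subject-level cluster effect following a normal distribution with a mean zero will serve as the random effect term". The authors will also consider "different covariance structures among repeated measurements and conduct model selection to determine the optimal model and covariance structure for the data". If the model does not converge, "we will adopt an ANOVA model to investigate the intervention efficacy at each measurement time point".

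Neither the plan nor the rest of the document names a visit term, a treatment-by-visit term or the baseline value of the outcome as a covariate. Nor does either say which waves enter as responses.

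**The concern.** A model with a single treatment coefficient and no time structure estimates one number per outcome. The design has two follow-up times that ask different questions: is there an effect when the episodes end, and is it still there three months later? The listed terms cannot answer these separately. The only analysis by time point is the ANOVA, which is used only after non-convergence and for which no baseline adjustment is named. Outcomes that converge could therefore report a visit average while others report per-visit effects.

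A second problem depends on something the plan leaves open. If T1 is a response row, a difference measured before randomisation, with expectation zero, is averaged into the treatment effect. The pilot exists to supply preliminary data for a larger trial, so it matters what its estimates represent.

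**Working it through.** The documents give no effect size, standard deviation, within-woman correlation, alpha or power, so there is no stated figure to reproduce.

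**Inputs.** From the documents: 33 women per arm; T1, T2 and T3 at 0, 1 and 4 months; T1 before randomisation. Assumed for illustration: unit variance, true effect d = 0.5 SD at both T2 and T3, correlation r = 0.3, 0.5 or 0.7, two-sided 5%, normal approximation, complete data.

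**Step 1: what the listed coefficient estimates.** Let d2 and d3 be the effects at T2 and T3. With a random intercept and no time term:

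- T1, T2 and T3 as responses: (0 + d2 + d3)/3. With d2 = d3 = 0.5 this is 0.333, two thirds of the truth. Adding only a visit main effect leaves it at 0.333.
- T2 and T3 as responses: (d2 + d3)/2. Effects of 0.5 and 0.5, 0.75 and 0.25, or 0 and 1.0 all give 0.5.

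Under other covariances the weight on T1 is the first element of V⁻¹1/(1′V⁻¹1). For AR(1) by months it is 0.31/0.32/0.35 at r = 0.3/0.5/0.7 per month. For AR(1) by visit order it is 1/(3 − r) = 0.37/0.40/0.43.

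A simulation of 150 trials (33 per arm, age and education included, r = 0.5, exchangeable) with true effects 0.6 at T2 and 0 at T3 agrees. The listed model averaged 0.21 with T1 as a response and 0.29 without it. A model with visit, treatment-by-visit and baseline returned 0.59 at T2 and −0.04 at T3.

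**Step 2: what baseline adjustment adds when T2 and T3 are the responses.** The unadjusted variance of a woman's T2-T3 average is v = (1 + ρ23)/2. Its covariance with T1 is c = (ρ12 + ρ13)/2. The adjusted variance is v − c².

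- Exchangeable: v = (1 + r)/2, c = r. At r = 0.5: 0.75 and 0.75 − 0.25 = 0.50, ratio 0.67.
- AR(1) by months: v = (1 + r³)/2, c = (r + r⁴)/2. At r = 0.5: 0.5625 and 0.5625 − 0.0791 = 0.4834, ratio 0.86.

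The standard error of a contrast is √((2/33) × variance), and power is Φ(d/SE − 1.96). A single adjusted visit has variance 1 − ρ², where ρ is its correlation with T1: r at both visits if exchangeable; r at T2 and r⁴ at T3 under AR(1) by months.

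| Quantity, r = 0.3/0.5/0.7 | Exchangeable | AR(1) by months |
|---|---|---|
| Variance ratio, T2-T3 average | 0.86/0.67/0.42 | 0.95/0.86/0.67 |
| Power, average, unadjusted | 71/65/60% | 81/77/70% |
| Power, average, adjusted | 77/82/92% | 83/83/86% |
| Power, T2 only, adjusted | 57/65/81% | 57/65/81% |
| Power, T3 only, adjusted | 57/65/81% | 53/53/55% |
| Power, single visit, unadjusted | 53% | 53% |

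For comparison, the listed model with T1 as a response has power of 46/38/33% under exchangeable correlation: estimate 2d/3, variance (1 + 2r)/3.

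**The case against.** The strongest reply is that the plan is a short summary and leaves the mean model open. It speaks of selecting the optimal model as well as the covariance structure, so a time term could still enter. That stands to this extent: a reader might infer that the fitted model must average over visits, and the documents do not establish that. But no candidate terms are named, and a term that selection might add is not a prespecified contrast.

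A reader might also infer that the effect will be diluted by a third. The plan never says T1 is a response row, so the dilution is conditional. For the same reason, the documents do not support saying that the later trial would be sized on a diluted coefficient; they promise only preliminary data for its design.

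A third tempting reading is that baseline adjustment brings a large gain at every visit. It does so under exchangeable correlation. If correlation decays by month, T3-only power barely moves from 53%, and the gain for the average is 2, 6 and 16 points (83 − 81, 83 − 77, 86 − 70).

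Finally, this is a pilot with no power target. That limits the stakes but does not settle what is being estimated.

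**Conclusion.** The point holds in a limited form. The plan names no term from which an effect at T2 or at T3 could be estimated. Followed as listed, it reports one visit-averaged coefficient per outcome. This rests on the text alone and needs no assumed input.

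The size of any harm does depend on assumptions. If T1 is a response, the coefficient is about two thirds of a common follow-up effect with a random intercept, complete data and a linear scale; the T1 weight is 0.31 to 0.43 under the AR(1) structures tried. If only T2 and T3 are responses, there is no bias for the average with complete data on a linear scale, and the loss is the T2/T3 separation plus precision that ranges from slight to substantial with the correlation pattern. Binary outcomes would be averaged on the link scale, where the two-thirds figure is not exact.

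This should be fixed before analysis. It does not undermine the pilot's design.

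**What to change.** Before analysis, state which waves are responses and prespecify one mean model:

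- T2 and T3 as responses, with treatment, visit, treatment-by-visit, the baseline outcome, age and education; or
- T1 to T3 as responses, with visit, treatment-by-visit, age and education, and the arms constrained to be equal at T1.

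The two agree closely for continuous outcomes but target different odds ratios for binary ones, so name one. Limit model selection to the covariance structure. Report the treatment contrast at T2, at T3 and their equally weighted average, each with a 95% confidence interval.

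Replace the ANOVA fallback with a baseline-adjusted comparison at T2 and at T3. For binary outcomes too sparse to model, report proportions by arm and the risk difference with a 95% confidence interval at each visit. Label it as a different scale from the model's odds ratio and as not adjusted for baseline.

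The cost is SAP wording; the baseline outcomes are already collected. The downside is a few more parameters in 66 women and some added risk of non-convergence for sparse binary outcomes. With an assumed prevalence of 2, 5 or 10%, the chance of no events among 33 women in one arm at one visit is (1 − p)³³ = 51, 18 or 3%. The fallback covers that case.

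### The Aim 2 analysis lets the outcome data choose the model as well as the covariance structure, and does not protect the form of the treatment effect from that choice

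*Combined protocol and SAP*

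**What the plan says.** The Statistical Analysis Plan paragraph, at the end of the combined document, sets out mixed-effects models for Aim 2. On fixed effects it says that "the treatment assignment status (intervention or control), age, education level will be included as the fixed effect terms". On the random part: "The subject-level cluster effect following a normal distribution with a mean zero will serve as the random effect term". The next sentence begins with covariance structures for the repeated measurements and goes on to say that the team will "conduct model selection to determine the optimal model and covariance structure for the data", with a reference to its own published work.

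The only other switch of model depends on convergence, not on fit: "if the model does not converge, we will adopt an ANOVA model to investigate the intervention efficacy at each measurement time point".

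The Study Description gives the design: "comparing 33 intervention- and 33 control Latinas at baseline", then "T2 (immediately post-intervention, 1 month) and T3 (3 months after the end of the intervention".

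The plan states no significance level, selection criterion, candidate models or primary treatment contrast. It declines multiplicity adjustment across outcomes because "our goal in this pilot study is to collect preliminary data to design future R01 study and proposal submission".

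**The concern.** The selection sentence names two things to be chosen from the data: the model and the covariance structure. Choosing the covariance structure affects the standard error of a treatment contrast that is already fixed. Choosing the mean model can change which treatment contrast is tested. Under the null, a treatment-by-visit term is kept by a fit criterion mostly when chance has separated the arms at some visit. If it is then tested as though it had been planned, the test rejects too often.

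The wider reading is a natural one. The study compares the arms over T1, T2 and T3, yet the listed fixed effects contain neither visit nor treatment-by-visit. Within the mixed model, the selection step is the only route by which those terms could enter.

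Two things are at stake. The treatment test for an outcome may carry more error than its nominal level suggests, and the disclosed lack of adjustment across outcomes does not cover choices made within one outcome. Also, nothing stops selection from running separately for each outcome. Condom use, HIV testing and PrEP outcomes could then be reported from different models with different treatment contrasts, which makes them hard to compare when designing the next trial.

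**Working it through.** **Plan's own figure.** None exists to reproduce. The plan gives no level, power, effect size or error rate. Only the allocation can be checked: 33 + 33 = 66.

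**Inputs.** From the documents: 33 women per arm, three visits, treatment, age and education as fixed effects. Assumed, because the plan is silent: two-sided 5% level, AIC or BIC as criterion, the candidate models, continuous Gaussian outcomes and complete data.

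**Step 1: closed form.** Let the choice lie between a main-effect model and a treatment-by-visit model, which has 2 more parameters. Under the null, take the main-effect statistic (chi-square, 1 df) and the interaction statistic (chi-square, 2 df) as independent. The larger model is chosen when the interaction statistic exceeds c, so P(select) = exp(−c/2).

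- AIC: c = 4, P(select) = exp(−2) = 0.135.
- BIC: c = 2 ln 66, P(select) = 1/66 = 0.015.

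If the chosen model's interaction test is the one reported, the false-positive rate is min(0.05, P(select)) + 0.05 × (1 − P(select)):

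- AIC: 0.05 + 0.05 × 0.865 = 0.093.
- BIC: 0.015 + 0.05 × 0.985 = 0.064.

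If the joint 3-df treatment test is reported instead (critical value 7.81), the AIC figure is P(interaction statistic > 4 and sum of both > 7.81) + 0.05 × 0.865 = 0.038 + 0.043 = 0.081.

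**Step 2: null simulations.** Simulation A used 3,000 trials per scenario, with AIC choosing among three mean models (treatment; plus visit; plus treatment-by-visit) and three covariance structures. Correlation was 0.5 to 0.6 and the visit shift 0 or 0.3 SD. Simulation B used 4,000 trials per scenario, with age and education as covariates and a true covariance of compound symmetry 0.5, AR(1) 0.6 or heteroscedastic unstructured. Its mean models were: as written; plus visit; treatment-by-visit (2-df test); treatment-by-post-baseline. Its Monte Carlo standard error is about 0.35 to 0.5 percentage points.

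| What is selected | False-positive rate |
|---|---|
| Nothing (fixed model, unstructured covariance) | B: 4.4% to 6.5% |
| Covariance only, AIC or BIC | A (AIC): 3.7% to 4.4%; B: 4.1% to 6.6% |
| Covariance and mean model, A's three candidates, joint test, AIC | A: 8.0% to 8.6% |
| Covariance and main effect + visit v treatment-by-visit, AIC | B: 9.1% to 10.2% |
| Same, BIC | B: 6.6% to 8.4% |
| Adding treatment-by-post-baseline, AIC | B: 11.0% to 11.9% |
| Same, BIC | B: 10.0% to 11.2% |
| All four mean models, AIC | B: 11.1% to 11.8% |
| Same, BIC | B: 8.6% to 9.0% |

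The closed form (8.1% to 9.3% for AIC, 6.4% for BIC) agrees with the two-model results in direction and approximate size.

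**Step 3: separating selection from multiplicity.** If any significant treatment coefficient is counted, simulation A gives 8.7% to 11.4% after selection. The matched comparison is a fully pre-specified treatment-by-visit model with no selection. Large-sample draws for its three coefficients (arm difference at T1 and the two interaction terms) give 12.5% for at least one significant result at correlation 0.5, and 12.1% for AR(1) 0.6. That count is already about 12% without selection, so it is not evidence of harm from selection and is left out of the size given here.

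**The case against.** The strongest reply is that the wider reading is not settled. The sentence opens with covariance structures, and the fixed effects have just been declared. If those terms stay and only the covariance is chosen, the error rate stays near 5%. This stands, and it is why the size is conditional. It does not remove the ambiguity: the text names the model separately from the covariance structure, and the cited earlier work does not make the plan self-contained.

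A reader might infer that the plan doubles the false-positive rate. The documents do not support that as a fact: they name no level, criterion or treatment-by-visit term, and the result depends on all three. A reader might also infer that the selected model's test will be reported with no allowance for selection. The plan is silent on this; it states no p-value or confidence-interval rule.

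The pilot purpose also softens the consequence. There is no confirmatory claim and no go/no-go threshold. The multiplicity that the plan openly accepts is larger: with independent outcomes at 5%, 1 − 0.95^4 = 18.5% for four and 1 − 0.95^7 = 30.2% for seven. That is a separate matter. Finally, several primary outcomes may be binary or counts, and the simulations do not cover those.

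**Conclusion.** The concern holds in conditional form. The plan allows an unspecified selection step to determine which treatment test is reported. If that step reaches the treatment-by-visit term, the per-outcome false-positive rate could rise from a nominal 5% to about 8% to 10% under AIC between two models, and to about 12% with more candidates. BIC between the same two models gives less, about 6% to 8%. If only the covariance structure is selected, the rate is about 4% to 7% and there is no material problem.

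All of this assumes a 5% two-sided level, the candidate models and criterion stated above, continuous outcomes and, in simulation B, no dropout. The possibility of different models for different outcomes follows from the text and needs none of these assumptions. Since the estimates feed the R01 design and the remedy is only wording, the change should be made.

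**What to change.** Replace the selection clause with:

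> For every outcome the fixed effects are treatment, visit, treatment-by-visit, age and education, set before outcome data are seen. One treatment contrast at one named time point is pre-specified as primary. Only the covariance structure is selected, from a listed set (unstructured, compound symmetry, AR(1)), by AIC with the fixed effects held constant. Continuous outcomes use REML with Kenward-Roger degrees of freedom; binary or count outcomes use the corresponding generalised mixed model with the same fixed effects. Any other mean model is labelled exploratory.

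The terms need to be named. Freezing the present list would leave out visit and treatment-by-visit, and the contrast would still be undefined. The team should fill in the contrast and time point itself.

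The change costs SAP wording only: no visits, participants or measures alter. The downside is less freedom to simplify the mean model, which could matter for a binary outcome with few events in 33 women per arm.

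### The ANOVA used if the mixed model does not converge makes no adjustment for the T1 outcome; a baseline-adjusted comparison at T2 and T3 would be a cheap, conditional improvement

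*Combined protocol and SAP*

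**What the plan says.** The Statistical Analysis Plan makes mixed-effects models the main analysis of intervention effect. It lists the fixed effects as follows: "the treatment assignment status (intervention or control), age, education level will be included as the fixed effect terms". A subject-level random effect is added, and several covariance structures are to be tried. The fallback comes next: "Alternatively, if the model does not converge, we will adopt an ANOVA model to investigate the intervention efficacy at each measurement time point". No covariate, baseline value or change score is named for that ANOVA, and no other section supplies one.

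Three other statements bear on it:

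- The Study Description says the trial will "conduct a randomized controlled pilot study to examine the change in primary outcomes".
- The same section describes "comparing 33 intervention- and 33 control Latinas at baseline (T1, pre-intervention), T2 (immediately post-intervention, 1 month) and T3".
- Under Baseline survey, the order of events is clear: "After participants complete the survey, they will be randomized by a member of the research team to the intervention or control group".

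The plan also says that multiplicity is left unadjusted because the pilot's purpose is to gather preliminary data for a future R01.

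**The concern.** T1 is measured before allocation, so it is a legitimate covariate that treatment cannot have affected, and the study already collects it from everyone. A separate ANOVA at T2 or T3 ignores it. If T1 predicts the follow-up value, the interval for the arm difference is wider than it need be. If the arms happen to differ at T1, part of that difference also appears at T2 and T3 as if it were intervention effect. Either would blur the estimates that the R01 design is to draw on. An aim framed as change makes the omission more noticeable.

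There is also a small wording point. The fallback covers every measurement point, and the Study Description counts T1 among them. Read literally, efficacy would be tested before any intervention had been given.

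**Working it through.** **Inputs from the documents.** The total is 66 women ("We will enroll 66 Latinas ages 18-44 years"), split 33 and 33 ("comparing 33 intervention- and 33 control Latinas"). T1 precedes randomisation. Age and education are covariates of the main model.

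**Assumptions, because the documents give none of these.** Continuous, normally distributed outcome with SD 1; true effect 0.5 SD; two-sided alpha 0.05; T1-to-follow-up correlation r of 0.3, 0.5 or 0.7; no dropout. Age and education are taken as uninformative and as using one degree of freedom each, so the ANCOVA has k = 3 covariate degrees of freedom with T1. The plan states no power or detectable difference, so there is no figure of its own to reproduce.

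**Validity of the ANOVA.** In 10,000 simulated trials with r = 0.5, the ANOVA rejected a true null 4.9% of the time. With a true effect of 0.50 its mean estimate was 0.50. The issue is therefore precision, not bias.

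**Variance.** In large samples the ratio of ANOVA to ANCOVA variance is 1/(1 − r²):

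- r = 0.3: 1/0.91 = 1.10
- r = 0.5: 1/0.75 = 1.33
- r = 0.7: 1/0.51 = 1.96

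With N = 66, estimating k random covariates costs a factor (63 − k)/63. For k = 3 this is 60/63 = 0.952, so the ratios become:

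- r = 0.3: 0.952/0.91 = 1.05
- r = 0.5: 0.952/0.75 = 1.27
- r = 0.7: 0.952/0.51 = 1.87

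If education enters in four categories (k = 5), they are 1.01, 1.23 and 1.81.

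**Break-even.** The two methods are equal when 1 − r² = (63 − k)/63, that is r = √(k/63). This gives 0.13 for k = 1, 0.22 for k = 3 and 0.28 for k = 5. Below these values the ANCOVA is slightly worse. At r = 0 with k = 3 its variance is 63/60 = 1.05 times that of the ANOVA.

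**Power and interval width** (simulation, 12,000 trials per cell, k = 3, 33 per arm):

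| | ANOVA | ANCOVA, r = 0.3 | r = 0.5 | r = 0.7 |
|---|---|---|---|---|
| Power | 52% | 54% | 61% | 78% |
| 95% half-width (SD) | 0.49 | 0.48 | 0.44 | 0.36 |

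A normal approximation with T1 as the only covariate and no charge for degrees of freedom gives 53% against 57%, 65% and 81%. The table is the more realistic version. With 26 per arm (about 20% dropout), power is about 42% for the ANOVA against about 43%, 51% and 67%.

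**Chance imbalance.** The standard error of the T1 difference is √(2/33) = 0.246 SD. An imbalance of that size shifts the unadjusted estimate by r × 0.246, which is 0.07, 0.12 or 0.17 SD.

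**The case against.** The strongest objection is that the gain may lie where the fallback is least likely to be used. In 600 simulated trials with a continuous outcome, 66 women, three visits, normal data and no dropout, a random-intercept model never failed to converge. Skewed data or richer covariance structures could do worse, but failure is more plausible for sparse yes/no outcomes, which the figures above do not cover. This stands, and it is why the point ranks low. So does the reminder that every magnitude rests on an assumed r: at r = 0.3 the gain is about two points of power.

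Three stronger readings are tempting, and the documents do not support them.

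- *The fallback is biased or invalid.* It is not: randomisation keeps the T2 and T3 comparisons unbiased on average.
- *The plan intends an efficacy test at T1.* The wording does not exclude one, but T1 is labelled as preceding the intervention, so T2 and T3 were probably meant. This is a matter of wording.
- *The fallback needs a special rule for binary outcomes.* The plan speaks of categorical variables only in general, when describing summary statistics ("the mean and standard deviation for continuous variables and frequency and proportion for categorical variables"), and the available text does not say which outcomes are binary. A rule switching between penalised logistic regression and an exact interval according to event counts would mix odds ratios with risk differences. In simulation it also lost power for sparse outcomes: for 5% against 15% prevalence, 29% with ANOVA and 20–22% with the rule; for 3% against 10%, 20% and 10–11%.

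The main model's listed fixed effects contain no time or treatment-by-time term. That is a separate and larger matter, and it neither supports nor removes this one.

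**Conclusion.** The point holds in a limited form. The fallback states no T1 adjustment, no other section supplies it, and the data needed are collected before randomisation. For a continuous outcome under the stated assumptions, the variance penalty runs from negligible (1.05 at r = 0.3) through moderate (1.27 at r = 0.5) to large (1.87 at r = 0.7). It reverses slightly below r of about 0.22. No claim is made for binary outcomes. The benefit arises only if the mixed model fails to converge, and how often that would happen is unknown. In an exploratory pilot this is a cheap, optional improvement, not a flaw that threatens the trial's conclusions.

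**What to change.** Replace the fallback sentence in the Statistical Analysis Plan with:

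> If no candidate covariance structure converges, the arms will be compared at T2 and at T3; for continuous outcomes this will be by ANCOVA adjusted for the T1 value of the outcome, age and education level. T1 will be described by arm and not tested.

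This needs no new data. It costs one degree of freedom for T1 and two or more for age and education if the ANOVA was to hold no covariates, with a slight loss of precision if r turns out to be low.
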